- l. Use of dual contraception (combined condom and effective non-barrier contraceptive use) during last vaginal sex
- m. Frequency of oral sex (in past 30 days)
- n. Frequency of anal sex (in past 30 days)
- o. Frequency of anal sex without condoms (in past 30 days)
- p. Frequency of using alcohol or drugs before having any type of sex (vaginal, anal, or oral) (in past 30 days)
- q. Pregnancy ambivalence*

3. What are the long-term (six months post-intervention period) impacts of the offer to participate in MARSSI (treatment) relative to the offer to participate in the control condition on the following sexual health behaviors, health outcomes, and theoretical antecedents of sexual health and health behavior?

- a. Depressive symptoms
- b. Frequency of vaginal sex (in past 30 days)
- c. Frequency of vaginal sex without effective non-barrier contraceptive use (in past 30 days)
- d. Frequency of emergency contraception use after vaginal sex (in past 30 days)
- e. Frequency of dual contraception (combined condom and effective non-barrier contraceptive use) during vaginal sex (in past 30 days)*
- f. Use of effective non-barrier contraception during last vaginal sex
- g. Use of condoms during last vaginal sex
- h. No effective contraception used during last vaginal sex
- i. Use of dual contraception (combined condom and effective non-barrier contraceptive use) during last vaginal sex
- j. Frequency of oral sex (in past 30 days)
- k. Frequency of anal sex (in past 30 days)
- l. Frequency of anal sex without condoms (in past 30 days)
- m. Frequency of using alcohol or drugs before having any type of sex (vaginal, anal, or oral) (in past 30 days)
- n. Current use of effective non-barrier contraception
- o. Frequency of vaginal sex without condoms (in past 30 days)
- p. Number of sexual partners (in past 3 months)

Analysis of primary and secondary outcomes in subgroups using ITT approach

What are the post-program, short-term, and long-term impacts of the offer to participate in MARSSI (treatment) relative to the offer to participate in the control condition on primary and secondary outcomes for subgroups defined by the following baseline data: 1) PHQ-8

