depressive symptoms score; 2) age; 3) race; 4) ethnicity; 5) gender; 6) Medicaid eligibility (proxy measure of healthcare access); 7) educational level; 8) recent receipt of sexual and reproductive health (SRH) information; 9) recent receipt of health services (mental health, SRH, and/or primary health care); 10) non-barrier contraceptive use; 11) main reason for using non-barrier contraception; 12) relationship status; 13) pregnancy intentions; and 14) feelings toward pregnancy.

CACE analysis of primary and secondary outcomes

What are the post-program, short-term, and long-term impacts of threshold participation in MARSSI on primary and secondary outcomes for a subgroup of participants assigned to treatment relative to a similar group of assigned to control?

2. Impact Study Design

This section provides a brief description of the study design and the process for creating intervention and comparison groups.

The BEhavior And Mindfulness Health (BEAM) study is an individual randomized controlled trial in which evaluators randomly assign eligible, consenting participants to intervention or comparison conditions at a one-to-one ratio. Random assignment occurs after participants' consent and before the provision of any programming or collection of baseline data.

Following submission of the baseline questionnaire, participants are implicitly informed of assignment through the discussion of next steps. Participants are enrolled on a rolling basis and randomized by the state where they would most likely seek reproductive health care and by the research coordinator who is enrolling them.⁴ See the *Random assignment process* section below for further details.

The treatment condition, MARSSI, is a motivational interviewing-based intervention designed specifically for adolescent and young adult (AYA) biologic females with depressive symptoms and sexual risk behavior. It aims to enhance motivation to change risky behaviors, provide skills to address depression's effects on behavior, and prompt and reinforce health-related affect regulation, cognitive behavioral skill use, and behavior change in daily life. MARSSI has three components: 1) a manualized counseling session with a sexual/reproductive health (SRH) counselor; 2) a mobile health application (mHealth app); and 3) a booster counseling session with the SRH counselor.

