To be eligible for enrollment, individuals must meet all of the following criteria: 1) biologically able to become pregnant; 2) 16-21 years of age;⁵ 3) fluent in English; 4) own a smartphone; 5) have the technical capacity to participate; 6) not currently pregnant; 7) not trying to become pregnant; 8) not have given birth during the six months preceding eligibility screening; 9) not be married or engaged to be married at the time of eligibility screening; 10) report having penile- vaginal sex in the past 3 months; 11) report having penile-vaginal sex at least once a week, on average; 12) score at least 8 on the PHQ-8 depression screening tool;⁶ 13) self-report visiting a reproductive health provider in the past two years;⁷ 14) report having done at least one of the following during the 3 months preceding eligibility screening: a) not used a condom every time they had sexual intercourse; b) used condoms, a diaphragm, cervical cap, spermicide, sponge, fertility awareness, or withdrawal as a primary form of birth control; c) had sexual intercourse with more than one person; d) had sexual intercourse within two hours after using drugs or alcohol; or e) been treated for a sexually transmitted infection/disease; 15) consent to participate in the study; and 16) not identified as fraudulent.⁸

The intent-to-treat sample (ITT) is comprised of eligible individuals who are enrolled into the study during the enrollment period (June 2021 to April 2023).

a. Random assignment process

- i. **Unit of randomization:** Random assignment occurs at the individual participant level.
- ii. **Random assignment procedure:** The Policy & Research Group (PRG) is responsible for all aspects of random assignment. Random assignment blocks of varying sizes assign participants to treatment or control condition at an equal (i.e., 1:1) assignment ratio. PRG produced this allocation list with an existing algorithm available in Stata (random allocation command, *ralloc*) and did so separately for each of the potential 255 study coordinator-state combinations.⁹ The allocation lists were produced by a PRG senior research analyst and stored on a secure server.

Electronic random assignment is conducted just prior to the administration of the online baseline questionnaire and is carried out by the study coordinators. Study coordinators were each given a sequential list of unique study IDs for every U.S. state. They assign a number (based on the state where the individual would seek

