As described in the *Estimation approach* subsection above, we will include covariates for the identified demographic characteristics and a baseline measure of the outcome of interest in each our benchmark models to increase the precision of our estimates and account for any small baseline differences between the treatment

and control groups.

iii. Additional covariates

We do not intend to include any further covariates beyond those specified in the *Estimation approach* subsection above.

Table 4. Covariates included in impact analyses

Covariate	Description of the covariate
Baseline primary outcome measures	
Frequency of vaginal sex without condoms in the past 30 days	
The risk outcome is operationalized as the number of times in the past 30 days a person reports having vaginal sex without using a condom.

	
The measure is calculated from the following item on the Participant Questionnaire:
 
 • In the past 30 days, how many times have you had vaginal sex without using a condom? 
The resulting variable is continuous with values that range from 0 to k, where 0 indicates that a person has not engaged in vaginal sex without a condom in the past 30 days, and k indicates the number of times the person has engaged in vaginal sex without a condom (risk behavior) in the past 30 days.
 
Note: All respondents who have baseline data and have provided a response to either this question or have indicated they have not had vaginal sex in the past 30 days will be included in the construction of this measure. Persons who indicate that they have not had vaginal sex in the past 30 days are coded as having vaginal sex without a condom zero times.

Current use of effective non-barrier contraception	
The protective outcome is operationalized as a dichotomous variable indicating whether a person reports currently using effective non-barrier contraception or not.

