Within the context of a randomized trial using a 1:1 assignment ratio, there is an expectation that principal stratum membership should be equally allocated to the treatment and control groups. In other words, if there are compliers in the treatment group, we would expect there exists a similar group of individuals in the control group who would have complied if the program had been offered to them. Whereas the conventional use of propensity scores aims to model treatment group membership (where treatment group membership is the same as intervention receipt), the aim here is to use propensity scores to model treatment receipt (compliance) in the treatment group and subsequently predict probability of principal stratum membership among members of the control group.

In accordance with Hill et al. (2002), to distinguish this latter prediction step for the control group, we refer to their probability of principal stratum membership as the principal score.⁴⁰ The core assumption in propensity score methods is that of conditional ignorable treatment assignment, or the assertion that treatment assignment is independent of the potential outcomes, given a set of observed covariates (Rosenbaum & Rubin, 1983). When we use a probability score to balance treatment and control groups to estimate CACE in an RCT, this assumption now applies to principal stratum membership (compliance). In other words, principal stratum membership is independent of the potential outcomes given the observed set of covariates (Jo & Stuart, 2009).

We will follow the steps outlined in Stuart & Jo (2015) to estimate the CACE using principal score weights. Briefly, these will include: 1) using the same baseline covariates used in the benchmark analysis to predict compliance among the treatment group; 2) predicting the probability of compliance (principal score) among members of the control group; 3) creating analytic weights reflecting the probability of compliance; and 4) estimating CACE by fitting the outcome model using the principal score weights. Consistent with the ITT analysis, we will use an appropriate regression model (OLS for continuous/scale measures, logit for dichotomous, count for frequency) for each outcome. We will include the following covariates in each model: age, gender, race, ethnicity, randomization blocks, and the baseline measure of the outcome.

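### The exploratory principal-score CACE models participation with covariates chosen for ITT precision, leaving out PHQ-8 and other available baseline predictors for all three primary outcomes

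*SAP*

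**What the plan says.** Section 4.f.i gives the identifying assumption: "principal stratum membership is independent of the potential outcomes given the observed set of covariates". Its first estimation step is "using the same baseline covariates used in the benchmark analysis to predict compliance among the treatment group". The section then lists the covariates for each model: "age, gender, race, ethnicity, randomization blocks, and the baseline measure of the outcome".

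The benchmark set comes from section 4.e.i and Table 4. Section 4.e.i justifies it by precision and by removing small chance imbalances between randomized arms. Section 4.e.iii closes it: "We do not intend to include any further covariates beyond those specified in the" estimation subsection. That sentence governs the ITT model and reaches the compliance model only because 4.f.i borrows the benchmark set.

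Other variables are available before treatment. Eligibility (section 2) requires participants to "score at least 8 on the PHQ-8 depression screening tool". Section 1.b plans analyses in "subgroups defined by the following baseline data: 1) PHQ-8" score, and the same list includes "Medicaid eligibility (proxy measure of healthcare access); 7) educational level; 8) recent receipt of sexual and reproductive health (SRH) information", recent health services, contraceptive use, relationship status, pregnancy intentions and feelings toward pregnancy. The self-efficacy items are in the Appendix A questionnaire.

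The introduction calls the CACE analyses exploratory and fixes no participation threshold. Section 4.f applies them to the full sample and to subgroups, alongside a two-stage least squares (TSLS) estimate (4.f.ii).

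**The concern.** In the ITT model, randomization removes confounding, so the choice of covariates affects mainly precision. In the compliance model nothing is randomized: some treated participants take part and some do not. The model must pick out controls who resemble the participants, and the control weights can reflect only the covariates in it. A list that suits the first purpose need not suit the second, and 4.f.i gives no reason for carrying it over.

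Depressive symptoms are the clearest candidate for a missing variable. Section 2 describes MARSSI as built for young people with such symptoms and aimed at their effect on behavior. If PHQ-8, or another omitted variable, is related both to participation and to sexual risk, part of the estimated complier effect is selection. The introduction says exploratory results will inform program development and may be published, so such an artefact could be read as a dose-response pattern.

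**Working it through.** The SAP gives no sample size, participation rate or effect size for the CACE, so there is no figure to reproduce. The check has two parts.

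**1. What the score contains.** The primary outcomes are sex without condoms, non-barrier contraception and number of partners. Their scores contain four demographics, blocks and the baseline value of that outcome. None contains PHQ-8, education, Medicaid eligibility, health-service receipt, pregnancy intentions or self-efficacy. Baseline contraceptive use enters for the contraception outcome. Baseline PHQ-8 enters when depressive symptoms are the outcome, and baseline self-efficacy when that scale is the outcome. None of the eight sensitivity analyses in 4.g enriches the compliance model, checks weighted balance or probes the ignorability assumption.

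**2. Size of bias from one omitted predictor.** All inputs are assumptions. Let U be a standardized omitted predictor, independent of the included covariates, and let the true effect be zero.

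- Participation: p(u) = 1 / (1 + exp(−(a − b·u))), with a set to give the assumed overall participation rate.
- Mean of U in treated compliers: m = E[U·p(U)] / E[p(U)]. Its weighted mean in controls is 0, because the weights ignore U.
- Bias = r × m, where r is the correlation of U with the outcome.

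| Participation | b per SD | m | r | Bias (SD) |
|---|---|---|---|---|
| 90% | 0.3 | −0.030 | 0.1 | −0.003 |
| 75% | 0.5 | −0.12 | 0.2 | −0.024 |
| 60% | 1.0 | −0.332 | 0.3 | −0.10 |

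These rows are the smallest, central and largest cases over participation of 60%, 75% and 90%, b of 0.3, 0.5 and 1.0, and r of 0.1, 0.2 and 0.3. The sign follows from assuming that participation falls as U rises; reversing that assumption reverses the sign. If b = 0 then m = 0, and if r = 0 then bias = 0.

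A separate simulation used 4,000,000 draws per scenario, participation of 50%, 70% or 85%, odds ratios of 1.0, 0.8 or 0.6 per SD, and outcome slopes of 0, 0.1 or 0.3. Where both links were present, the absolute bias was 0.003 to 0.071 residual SD. With U added to the compliance model it was 0.000 in every scenario.

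**Allowing for the baseline outcome.** Now let U have correlation 0.2 with the baseline outcome, which is in the model. With baseline-to-follow-up correlation q, the central case becomes about 0.12 × (0.2 − 0.2q):

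- q = 0.3: 0.12 × 0.14 = 0.017 SD
- q = 0.5: 0.12 × 0.10 = 0.012 SD
- q = 0.7: 0.12 × 0.06 = 0.007 SD

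**The case against.** The strongest reply is that this is one of two methods in an analysis the plan labels exploratory, and that effectiveness will be judged on the primary ITT estimates. That stands, and it limits the weight of the point.

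Several stronger readings are tempting, and the SAP does not support them.

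- A reader might infer that compliers *are* compared with the wrong controls. This needs an omitted variable linked to both participation and outcome given the included covariates. The SAP has no data on either link.
- A reader might infer a bias in favor of MARSSI. That requires more symptomatic participants to take part less. Since the program is designed for them, they might take part more, and the bias would reverse.
- A reader might infer that PHQ-8 is missing throughout. It enters as the baseline measure for depressive symptoms.
- A reader might add the figures across predictors. They are one-at-a-time values, and correlated predictors such as PHQ-8 and coping self-efficacy overlap.
- A reader might count the pairing with TSLS as a further harm. TSLS does not need this ignorability assumption, so it is a cross-check. It is not an assumption-free one. In Table 1 the main session alone scores 2 of 4, or 50%, below the 75% participation measure. At a threshold that high, some TSLS non-compliers would have received active content, which strains the exclusion restriction.

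The reply that more predictors cost more than a little also has force. The model is fitted in the treatment arm only, with up to 255 − 1 = 254 block dummies, at several participation levels and within subgroups. Blocks with no treated participant cannot be estimated, and sparse blocks may predict participation perfectly. This supports a short, penalised list; it does not support keeping the demographic one.

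**Conclusion.** The point holds as a weakness of specification. The compliance model uses covariates selected for another purpose, and for all three primary outcomes it leaves out PHQ-8 and other available variables that could bear on both participation and outcome. Whether bias results, and in which direction, cannot be settled from the SAP. Under the assumed inputs the bias is zero if either link is absent and otherwise modest: about 0.003 to 0.10 SD for one predictor, with the upper end needing all three unfavorable inputs at once, and less where the baseline outcome already carries part of the predictor. The change is worth making because it is cheap and nothing else in the plan covers the gap. The ITT conclusions do not depend on it.

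**What to change.** In step 1 of 4.f.i, prespecify a compliance model with the benchmark covariates plus a short list of collected baseline predictors: PHQ-8 first, then education, Medicaid eligibility, recent health-service receipt, pregnancy intentions and feelings, and baseline self-efficacy. Use a parsimonious or penalised fit, and penalise or pool the sparse block dummies in the treatment-arm model. Report weighted balance of treated compliers against weighted controls on these variables at each participation level analysed.

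Leave the ITT benchmark covariates unchanged. Keep TSLS, described as a cross-check that rests on different assumptions.

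The cost is SAP wording and a few lines of code, with no new data. The downside is somewhat more variable weights, especially in subgroups. Fixing the list in advance also prevents a later choice among compliance models.

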The benefit of the TSLS model is that it allows for the inclusion of baseline covariates that predict both participation and the outcome, which can help further reduce the amount of error in the estimation and possibly reduce bias due to exclusion restriction violations.⁴³ As with the benchmark approach and principal score method approach, we will include the following covariates in both stages: age, gender, race, ethnicity, a baseline measure of the outcome of interest, and a series of dummy variables representing the randomization blocks.

g. Sensitivity analyses

We will conduct sensitivity analyses to test the robustness and validity of our benchmark approaches outlined above. These include: 1) estimating program effects using OLS regression without baseline covariates and blocking variables; 2) implementing alternative models to test for bias; 3) excluding baseline covariates; 4) not imputing or adjusting for missing data; 5) excluding unreliable data; 6) excluding outliers; 7) condensing data collection windows to exclude late responders; and 8) using alternative model specifications to estimate program effects.

⁴¹ Angrist, J., & Imbens, G. W. (1995). Two-stage least squares estimation of average causal effects in models with variable treatment intensity. *Journal of the American Statistical Association*, 90(430), 431–442. <https://doi.org/10.2307/2291054>.

⁴² Connell, A. M. (2009). Employing complier average causal effect analytic methods to examine effects of randomized encouragement trials. *The American Journal of Drug and Alcohol Abuse*, 35(4), 253–259. <https://doi.org/10.1080/00952990903005882>.

Schochet, P. Z., & Chiang, H. S. (2011). Estimation and identification of the complier average causal effect parameter in education RCTs. *Journal of Educational and Behavioral Statistics*, 36(3), 307–345. <https://doi.org/10.3102/1076998610375837>.

Stuart, E. A., Perry, D. F., Huynh-Nhu, L., & Lalongo, N. S. (2008). Estimating intervention effects of prevention programs: Accounting for noncompliance. *Prevention Science*, 9(4), 288–298. <https://doi.org/10.1007/s11121-008-0104-y>.

⁴³ Jo, B. (2002). Statistical power in randomized intervention studies with noncompliance. *Psychological Methods*, 7(2), 178–193. <https://doi.org/10.1037/1082-989x.7.2.178>.

- i. **Difference of means.** Our benchmark approach is to include baseline covariates and blocking variables in an OLS regression model to improve the precision of our effect estimates. Assuming our sample is sufficiently large, this approach should generate unbiased estimates.⁴⁴ To test this, we will conduct sensitivity analyses that use OLS and only the treatment indicator included as an independent variable. This approach should approximate a difference of means t-test. We will report any substantive differences in the results section of the final manuscript and analytic findings for both approaches will be presented alongside each other in an appendix.
- ii. **Alternative models.** Our benchmark approach includes covariates and accounts for blocking procedures either using fixed effects for the study coordinator-by-state assignment blocks or an IPTW approach that is similar but does not zero-weight single-case cells. This strategy offers a compromise between the unbiasedness of the difference-of-means approach and the added precision and statistical power offered by regression adjustment. Heterogeneous treatment effects, however, remain a possible threat to this approach. As such, we propose to fit a model that constructs a treatment effect from a weighted average of a fully saturated OLS regression model. We will use the weighted least squares version of this model proposed by Lin (2013, p.10). We will report any substantive differences in the results section of the final manuscript and analytic findings for both approaches will be presented alongside each other in an appendix.
- iii. **Without baseline covariates.** Our benchmark approach is to include baseline covariates in our model to improve the precision of our estimates. To test this, we will conduct sensitivity analyses that involve running identical empirical models without the baseline covariates included. We will report any substantive differences in the results section of the final manuscript and analytic findings for both approaches will be presented alongside each other in an appendix.
- iv. **Without adjusted baseline data.** As outlined in the *Missing data approach* section, our benchmark approach is to adjust baseline data as published guidance suggests that this may produce unbiased impact estimates and maximize the use of available data. We will test this by way of sensitivity analyses that involve running identical empirical models without the adjusted data. As outlined in the *Assessment of baseline equivalence* section, we will also produce diagnostic estimates of baseline equivalency on the baseline outcome variables according to our benchmark approach. We will report any substantive differences identified in these analyses in the results section of the final manuscript and analytic findings for both approaches will be presented alongside each other in an appendix.
- v. **Without unreliable data.** As discussed in the *Data cleaning* section, data for cases that are deemed unreliable are flagged, but still included in benchmark analyses. We will also conduct sensitivity analyses that involve running identical empirical models with the unreliable data excluded. We will report any substantive differences in the

⁴⁴ Angrist, J. D., & Pischke, J.-S. (2009). *Mostly harmless econometrics: An empiricist's companion*. Princeton: Princeton University Press; Lin, W. (2013). "Agnostic Notes on Regression Adjustments to Experimental Data: Re-Examining Freedman's Critique" *The Annals of Applied Statistics*. 7(1) 295-318.

results section of the final manuscript and analytic findings for both approaches will be presented alongside each other in an appendix.

- vi. **Without outliers.** As discussed in the *Data cleaning* section, extreme data values are investigated and flagged as outliers. Our benchmark analytic approach is to include data flagged as outliers (i.e., extreme values that are not considered invalid) in analysis. We will also conduct sensitivity analyses that exclude these data. We will report any substantive differences in the results section of the final manuscript and analytic findings for both approaches will be presented alongside each other in an appendix.
- vii. **Condensed data collection windows.** Our benchmark approach is to include follow-up data from all participants who completed a questionnaire during their open data collection window, regardless of the time point in that window when it was completed. Data collection windows are broad to minimize attrition from the analytic sample. To examine whether or not this influences our results – and, in particular, whether or not study participants who respond later report different outcomes from those who respond earlier – we will conduct an analysis that examines the difference, if any, in response time between treatment and control participants and compares impact estimates for analytic samples without late responders. Late responders will be defined as those participants who complete their long-term questionnaire more than one month after the initiation of the three-month data collection window. We will report any substantive differences in the results section of the final manuscript and analytic findings for both approaches will be presented alongside each other in an appendix.
- viii. **Statistical modeling.** We have proposed using OLS regression as the benchmark statistical method for producing impact estimates. We will conduct analyses to test robustness of this choice and to assess whether there are substantive differences in the point estimates of interest produced by OLS and alternative estimators.⁴⁵ Specifically, for each research question, we will compare OLS estimates with those derived from models that may fit the distribution of the data better. For the two count outcomes (frequency of having vaginal sex without condoms and number of sexual partners), the treatment effect will be estimated with an appropriate count model (using Stata); for the dichotomous outcome, the effect will be estimated using a logit model.⁴⁶ If there is a substantive difference in the impact estimates of interest, we will report the results of each.

h. Bayesian interpretation

In addition to assessing our primary research question findings using a traditional frequentist approach, we will supplement our presentation of impact estimates with a Bayesian interpretation based on posterior probabilities of program effectiveness. To do

⁴⁵ To account for potential violations of model assumptions (e.g., heteroskedasticity, overdispersion), we will use robust standard errors in all analyses.

⁴⁶ For count models, we will assess model fit using diagnostic model-fit methods, including the Stata command countfit, AIC and BIC model fit statistics, and by assessing predicted versus observed count probabilities for competing models. See Hilbe, J. M. (2014). *Modeling count data*. New York: Cambridge University Press.

this, we will rely upon the BAyesian Interpretation of Estimates (BASIE) framework.⁴⁷ The prior distributions for our Bayesian estimate will be informed by the meta-analysis of teen pregnancy prevention intervention program effects conducted by Juras et al.⁴⁸ We will calculate the precision-weighted average of the traditional estimate (i.e., shrunken estimate) based on this prior evidence using the BASIE probability tool provided by Deke et al. The shrunken estimates will be treated as sensitivity analyses to our traditional estimates. We will report the shrunken estimates alongside the estimates derived from our impact study data and interpret them using posterior probabilities.

⁴⁷ Deke, J., Finucane, M., & Thal, D. (2022). The BASIE (BAyeSian Interpretation of Estimates) Framework for Interpreting Findings from Impact Evaluations: A Practical Guide for Education Researchers. Toolkit. NCEE 2022-005. *National Center for Education Evaluation and Regional Assistance*.

⁴⁸ Juras, R., Kelsey, M., Steinka-Fry, K., Lipsey, M., Layzer, J., & Tanner-Smith, E. (2022). Meta-analysis of Federally Funded Adolescent Pregnancy Prevention Program Evaluations. *Prevention Science*, 23(7), 1169-1195.

5. Additional planned analyses⁴⁹

In addition to the primary and secondary research questions described above, we intend to investigate the effect of mediating factors on primary outcomes of interest and one secondary outcome of interest.

Effects of Mediators on Primary and Secondary Outcomes of Interest

- a. What are the short-term (three months post-intervention) and long-term (six months post-intervention) impacts of the offer to participate in MARSSI (treatment) relative to the offer to participate in the control condition on participants' reported *frequency of having vaginal sex without condoms* considering the following potential mediators:
 - a. Sexual communication self-efficacy
 - b. Condom planning self-efficacy
 - c. Condom knowledge
 - d. Contraceptive knowledge
- b. What are the long-term (six months post-intervention) impacts of the offer to participate in MARSSI (treatment) relative to the offer to participate in the control condition on participants' reported *frequency of having vaginal sex without condoms* considering the following potential mediators:
 - a. Motivation to use condoms
- c. What are the short-term (three months post-intervention) and long-term (six months post-intervention) impacts of the offer to participate in MARSSI (treatment) relative to the offer to participate in the control condition on participants' reported *use of effective non-barrier contraception* considering the following potential mediators:
 - a. Sexual communication self-efficacy
 - b. Contraceptive planning self-efficacy
 - c. Contraceptive knowledge
- d. What are the long-term (six months post-intervention) impacts of the offer to participate in MARSSI (treatment) relative to the offer to participate in the control condition on participants' *use of effective non-barrier contraception* considering the following potential mediators:
 - a. Motivation to use prescription birth control
- e. What are the short-term (three months post-intervention) and long-term (six months post-intervention) impacts of the offer to participate in MARSSI (treatment) relative to the offer to participate in the control condition on participants' reported *number of sexual partners* considering the following potential mediators:
 - a. Sexual communication self-efficacy
 - b. Condom planning self-efficacy
 - c. Contraceptive planning self-efficacy
 - d. Coping self-efficacy
 - e. Condom knowledge
 - f. Contraceptive knowledge

⁴⁹ Note that we have not included a research question examining how COVID-19 may have influenced program implementation and participant outcomes because the MARSSI intervention was implemented exclusively in a virtual format during the full course of the study. As such, we are not able to explore differences between in-person and online implementation.

- f. What are the are the long-term (six months post-intervention) impacts of the offer to participate in MARSSI (treatment) relative to the offer to participate in the control condition on participants' reported *number of sexual partners* considering the following potential mediators:
 - a. Motivation to purposefully abstain from sex
- g. What are the are the short-term (three months post-intervention) and long-term (six months post-intervention) impacts of the offer to participate in MARSSI (treatment) relative to the offer to participate in the control condition on participants' reported *depressive symptoms* considering the following potential mediators:
 - a. Coping self-efficacy

These questions pertaining to potential mediators will be explored only if the main relationship between treatment and the primary outcome of interest is found to be statistically significant at the $p < .05$ level. In this scenario, we will conduct mediation analysis to estimate the total, indirect, and direct effects of treatment on the outcomes listed above, considering the specified mediators, using an appropriate modeling approach based on the type of outcome being explored.

